**Protocol for non-interventional studies based on existing data:**

Document Number:	c12696196-01
BI Study Number:	1160.219
BI Investigational Product(s):	PRADAXA (dabigatran)
Title:	Validation of predictors for oral anticoagulant medication choice using EMR data (Phase 3b of the BI/BWH Pradaxa study program)
Protocol version identifier:	1.0
Date of last version of protocol:	02 November 2016
PASS:	No
EU PAS register number:	Not available yet
Active substance:	Dabigatran etexilate
Medicinal product:	Pradaxa
Product reference:	EU/1/08/442/001-019
Procedure number:	EMEA/H/C/000829
Joint PASS:	Not applicable
Research question and objectives:	
The research question is whether select patient characteristics that may be incompletely captured by insurance claims data, differ between dabigatran and warfarin initiators.
 
Objectives:
 
 
1) Descriptive: To identify select clinical covariates from electronic medical records that might be associated with initiation of oral anticoagulant medications (dabigatran or warfarin) in NVAF patients at risk for stroke and are not usually well captured in the associated claims database
 
2) Prediction Rule: To assess how well EMR-based clinical characteristics can be captured on the basis of claims data only
 
3) Assess Balance: To assess the potential for unmeasured confounding in dabigatran vs warfarin comparative effectiveness and safety studies based on administrative claims
 

Proprietary confidential information © 2016 Boehringer Ingelheim International GmbH or one or more of its affiliated companies

	databases
Country(-ies) of study:	US
Author:	
Marketing authorisation holder(s):	Boehringer Ingelheim
MAH contact person:	
Date:	02 November 2016
Page 2 of 55	
Proprietary confidential information © 2016 Boehringer Ingelheim International GmbH or one or more of its affiliated companies. All rights reserved. This document may not - in full or in part - be passed on, reproduced, published or otherwise used without prior written permission	

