#### 9.3.2.2 Secondary outcomes

- Duration of atrial fibrillation
- History of adherence
- History/duration of hypertension
- Uncontrolled Hypertension (for HAS-BLED)
- History/duration of CHF
- Prior TIA
- Diabetes
- Hyperlipidemia
- HAS-BLED Score
- Use of antiplatelets or NSAIDs (needed for HAS-BLED)

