**Table 1 Outcome definitions**

Outcome	Definition	Present	Categories if present
Primary			
Obesity	Calculated BMI >30 or recorded "obesity"	Y/N	Obese, not-obese based on note of obesity or recorded BMI>30.
Smoking	Any note on smoking	Y/N	Current & past combined and nonsmoker & not noted combined.
Alcohol consumption	Any note on alcohol use	Y/N	Alcohol use (any); No use
Abnormal renal function	Any note of: Dialysis, renal transplant Serum Creatinine >1.3 mg/dL	Y/N	
Bleeding history or predisposition	Any note of: Major bleeding requiring hospitalization or blood transfusion or causing a decrease in hemoglobin level of > 2 g/L	Y/N	
Renal function	Estimated GFR closest to index dispensing	Y/N	The value
Serum Creatinine	Closest to the index date	Y/N	The value
Abnormal liver function	Any note of: Liver disease, cirrhosis, Active hepatitis C Active hepatitis B Active hepatitis A AST/ALT >3X upper limit of normal Absence of any note would be considered as absence of the disease	Y/N	

[figure not shown]
Table 1 (cont'd) Outcome definitions

[figure not shown]
Outcome	Definition	Present	Categories if present
Secondary			
Duration of atrial fibrillation	Years/months prior to initiation of dabigatran/warfarin	Y/N	Number of months prior to index date for the earliest note
History of adherence	Any note of patient adherence/lack thereof in EMR	Y/N	Non-adherent Adherent
History/duration of hypertension	Any note of: Hypertension SBP >120 mmHg Hypertension drugs	Y/N	Number of months prior to index date for the earliest date
Uncontrolled Hypertension (for HASBLED)	SBP >160 mmHg using the most recent information prior to index date	Y/N	
History/duration of CHF	Any note of: CHF	Y/N	Number of months prior to index date for the earliest note
Prior TIA	Any note of TIA	Y/N	Also, number of months prior to index date if noted
Diabetes	Any note of: Diabetes Absence of any note of diabetes will be considered as absence of the disease	Y/N	
Hyperlipidemia	Any note of; Hyperlipidemia, dyslipidemia, LDL>130 mg/dl		
HAS Bled Score	As recorded (if recorded) or calculated from EMR data. [REDACTED]	Recorded/ calculated /none	The value
Use of antiplatelets or NSAIDs (needed for HASBLED)	Use of aspirin, clopidogrel, prasugrel, ticagrelor or NSADs (within 1 month or on the index date)	Y/N	
INR	Closest to the index date	Y/N	The value

[figure not shown]

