**Table 2** **Components of HAS-BLED bleeding risk score\***

[figure not shown]
HAS-BLED item	Points
Hypertension (uncontrolled)	1
Abnormal renal and liver function (1 point each)	1 or 2
Stroke	1
Bleeding history or predisposition (anemia)	1
Labile INR	1
Elderly	1
Drugs or alcohol (1 point each)	1 or 2

[figure not shown]
\*HAS-BLED score is calculated by adding the specified points for each of the conditions listed. [\[R10-6394\]](#)

[figure not shown]

[figure not shown]

[figure not shown]

[figure not shown]

[figure not shown]

[figure not shown]

[figure not shown]

[figure not shown]

[figure not shown]

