## **9.9 LIMITATIONS OF THE RESEARCH METHODS**

This is a validation study and we are not assessing the association between EMR-based patient characteristics and clinical outcomes.

The source claims data include limitations with respect to certainty of the capture of exposure, covariates, and outcomes. As a comprehensive insurance database, essentially all billable medical services will result in claims for reimbursement, so that the certainty of capture is tied to likelihood of a claim being submitted to the insurer.

Although more information on covariates is captured in EMR, some data will be missing in EMR as well. In addition, information is assessed during routine medical care (not in a standardized way) and some variation in assessment persists but cannot be studied within the scope of the study.

As in any EMR source, there could be potentially small number of dabigatran initiators and they might not represent dabigatran initiators in the general population. In addition, the data sources for this study are commercial US data sources (based on employed people and their dependents), so they tend to over-represent working-age people. The data are supplemented with elderly through patients with certain types of Medicare coverage (Medicare Advantage); however, elderly with Medicare Advantage tend to be healthier and more likely to still be employed as compared to elderly with other types of Medicare. These features of data may further limit the generalizability in that the results will be most generalizable to US people who are employed. [[P13-03077](#), [P13-03078](#)]

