### *Cohort formation*

Initiators of dabigatran and warfarin will be matched on their PS to initiate the treatment of interest (dabigatran) and the calendar quarter of initiation. PS will be derived from predicted probabilities of treatment initiation with dabigatran as compared to warfarin estimated in a logistic regression model that includes all claims-based covariates identified in this protocol [REDACTED]. The PS will be used to match dabigatran initiators to warfarin initiators on a 1:1 fixed ratio basis using a nearest-neighbor algorithm.

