#### **9.11.2 EMR-linked subset**

From the PS-matched cohorts we will identify patients who have EMR data available. Most analyses will be performed in this group. We expect that the EMR-linked subset is a random subset so that the covariate balance achieved by propensity score matching in the overall cohorts will be retained in the EMR subsets. However, due to chance, some imbalances in baseline characteristics may occur. We will check the average PS among the linked subset and inspect covariates among them prior to proceeding with the analysis. In the event of imbalances, we will proceed with analyses outlined after stratifying by the propensity score.

Figure 1 Patient Selection Flow Chart

We will provide Truven with linkage IDs and exposure indicators. Within the EMR-linked subset, Truven will evaluate the balance of the EMR clinical characteristics across exposure groups (see [section 9.7 Data Analysis](#) for detailed description).

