## **9.12 BIAS**

Various design and analysis methods will be implemented to reduce the potential for bias in the study. We will employ new-user cohorts of dabigatran and warfarin in order to address differences that might arise in the comparison of newer and older treatments, such as survivor bias and attrition of susceptibles. The comparator cohort will be formed warfarin initiators with similar clinical profiles to dabigatran initiators to reduce confounding by indication. We will employ propensity score matching of dabigatran and warfarin cohorts in order to improve the balance of the cohorts with respect to numerous variables.

As a validation study, the aim of this study is to assess the magnitude of potential confounding that might be present in the main cohort study as a result of non-claims characteristics that are both associated with choice of anticoagulant and predictive of study outcomes.

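### One yes/no item merges aspirin, NSAIDs and prescription antiplatelets: adequate for HAS-BLED, but it can mask an imbalance in the part that claims are likely to miss

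*Combined protocol and SAP*

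**What the plan says.** Table 1 defines the item as "Use of aspirin, clopidogrel, prasugrel, ticagrelor or NSADs (within 1 month or on the index date". It is coded Y/N and the categories column is blank. Section 9.3.2.2 lists it among the secondary outcomes as "Use of antiplatelets or NSAIDs (needed for HAS-BLED". Table 2 scores the corresponding HAS-BLED component as "Drugs or alcohol (1 point each", so the score needs only one drug flag.

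The item is more than an input to a score. Section 9.3.2 treats the listed EMR characteristics as outcomes of this validation study, and Objective 1 in section 9.7.1 describes them by treatment group in Table 9.

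The title page states the research question as "whether select patient characteristics that may be incompletely captured by insurance claims data, differ between dabigatran and warfarin initiators". Section 9.12 gives the target as "non-claims characteristics that are both associated with choice of anticoagulant and predictive of study outcomes". On what claims contain, section 9.9 says that "the certainty of capture is tied to likelihood of a claim being submitted to the insurer".

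The groups are matched on a propensity score from a "logistic regression model that includes all claims-based covariates identified in this protocol". Section 9.11.2 expects that "the covariate balance achieved by propensity score matching in the overall cohorts will be retained in the EMR subsets". The visible text describes no analysis of this item by drug or drug class.

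**The concern.** By the plan's own rule, a drug is visible in claims to the extent that a claim is submitted for it. The drugs in this item probably differ in that respect. Clopidogrel, prasugrel and ticagrelor are normally dispensed on prescription and leave a claim. Aspirin and many NSAIDs can be obtained without one. The documents do not say this, so it is an assumption here. If it holds, the second group is what the EMR adds, yet the item codes a patient on clopidogrel alone and a patient on non-prescription aspirin alone identically. A patient on both counts once.

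Two things follow for the confounding assessment. A balanced composite does not show that the part missed by claims is balanced. An unbalanced composite does not by itself show which part is responsible. Objective 2 inherits the problem: claims might predict the composite well because of the dispensed antiplatelets, while saying little about aspirin. Objective 3 inherits it if the composite is the covariate entered. Aspirin and NSAID use bears on bleeding, so undue reassurance on this item would matter to the main claims study.

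**Working it through.** **Inputs from the plan.** Section 9.5 gives about 20,000 matched patients per group and 5.5% linkage. 0.055 × 20,000 = 1,100 per group, which reproduces the plan's figure. The abstract gives 15,000 per group. 0.055 × 15,000 = 825, so both sizes are used.

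**Assumed inputs.** The documents give no drug prevalences, significance level or detectable difference. I take aspirin use as *a*₁ = 35% and *a*₀ = 30%, the other listed drugs combined at prevalence *r* in both groups, and a two-sided 0.05 test.

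**Formulas.**
- Composite under independent use: *c* = 1 − (1 − *a*)(1 − *r*), so *c*₁ − *c*₀ = (1 − *r*)(*a*₁ − *a*₀).
- Standardized difference: (*p*₁ − *p*₀) / √{[*p*₁(1 − *p*₁) + *p*₀(1 − *p*₀)]/2}.
- Power: normal approximation for two proportions, pooled variance under the null and unpooled under the alternative.

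**Aspirin alone.** The difference is 5.0 points. The standardized difference is 0.05 / √[(0.2275 + 0.2100)/2] = 0.107. Power is 0.71 at 1,100 per group and 0.58 at 825.

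**Composite, other drugs balanced and independent of aspirin.**

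| *r* | Composite | Difference (points) | Standardized difference | Power, 1,100 | Power, 825 |
|---|---|---|---|---|---|
| 10% | 41.5% vs 37.0% | 4.5 | 0.092 | 0.58 | 0.46 |
| 20% | 48.0% vs 44.0% | 4.0 | 0.080 | 0.47 | 0.37 |
| 30% | 54.5% vs 51.0% | 3.5 | 0.070 | 0.38 | 0.30 |
| 40% | 61.0% vs 58.0% | 3.0 | 0.061 | 0.30 | 0.24 |

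**One case by class.** Take prescription antiplatelets at 12% and NSAIDs at 15% in both groups. The composite is 1 − 0.65 × 0.88 × 0.85 = 51.4% vs 1 − 0.70 × 0.88 × 0.85 = 47.6%, with a standardized difference of 0.075. If those proportions were observed at 1,100 per group, the 95% interval for the aspirin difference would be 1.1 to 8.9 points and for the composite −0.4 to 7.9 points. At 825 per group they would be 0.5 to 9.5 and −1.1 to 8.6 points.

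**Where the loss disappears** (same aspirin figures, *r* from 10% to 40%):
- If different patients use aspirin and the other drugs, the composite is *a* + *r*. The difference stays at 5.0 points and the standardized difference is 0.100 to 0.112.
- If the other drugs are 3 points higher in the group with more aspirin, the composite difference is 6.5 points at *r* = 10%, falling to 4.9 at *r* = 40%. That is larger than for aspirin alone, or about equal to it.

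**The case against.** The strongest reply is that the item does what its label says. It is a secondary outcome marked as needed for HAS-BLED, and the score gives drugs one point. That stands: the composite is not an error for the score.

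A second reply is that matching should balance whatever claims capture, so an imbalance in the composite would point to what claims miss, and Objective 2 shows how far claims explain the item. This has force and limits the attribution point to harder, not impossible. It depends on these drugs being propensity-score covariates, which cannot be checked because the covariate tables are not visible. It also does nothing for a balanced composite.

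Third, the visible text sets no threshold for imbalance, and every prevalence above is assumed. That stands too: the figures illustrate a mechanism and do not forecast the result.

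Two stronger readings are tempting. A reader might infer that the composite necessarily dilutes an aspirin imbalance. It does not, as the cases with different users and same-direction imbalance show. A reader might also suppose that an opposite imbalance in prescription antiplatelets could cancel an aspirin imbalance. That sits badly with matching on claims covariates and with the inspection of covariates in the linked subset before analysis (section 9.11.2). Nothing in the documents supports assuming such a gap.

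Nor is the split simply aspirin against prescription drugs. NSAIDs may also be obtained without a claim, and aspirin may be prescribed.

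**Conclusion.** The point holds as a worthwhile, low-cost improvement to a secondary outcome. The merged item is adequate for HAS-BLED but too coarse for the confounding assessment, because it can mask an imbalance in use that claims miss and blurs the source of any imbalance it does show. Under balanced, independent use of the other drugs it keeps a fraction 1 − *r* of the aspirin difference, so 90% at *r* = 10% and 60% at *r* = 40%. For a 5-point aspirin difference at the linked sizes the plan implies, that is a material loss of power.

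The conclusion rests on three assumptions: that some aspirin and NSAID use leaves no claim, that the drugs overlap within patients roughly as under independence, and that the other drugs are about equally common in both groups. The masking and attribution argument needs only the first. The sizes need all three, together with the assumed prevalences.

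**What to change.** Keep the combined Y/N item for the HAS-BLED drug point. In addition:

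- Define aspirin, NSAIDs and prescription antiplatelets (clopidogrel, prasugrel, ticagrelor) as separate items in Table 1, and give each a row by treatment group in Table 9.
- Within the linked subset, cross-classify EMR-recorded aspirin and NSAID use with claims dispensings of the same class over the same window, so that use without a claim is shown by group.
- Enter the components separately in the Objective 2 and Objective 3 models.

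The cost is a few table rows and models, plus one claims–EMR cross-tabulation. The rows should be cheap because the flag is already defined from named drugs and classes. The cross-tabulation takes somewhat more work: under section 9.11.2 the data vendor evaluates EMR balance after receiving linkage IDs and exposure indicators, so class-level dispensing flags would have to be available at that step. Objective 2 already models EMR items on claims covariates, so joining the two sources is within the plan's scope.

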**Table 2** **Components of HAS-BLED bleeding risk score\***

[figure not shown]
HAS-BLED item	Points
Hypertension (uncontrolled)	1
Abnormal renal and liver function (1 point each)	1 or 2
Stroke	1
Bleeding history or predisposition (anemia)	1
Labile INR	1
Elderly	1
Drugs or alcohol (1 point each)	1 or 2

[figure not shown]
\*HAS-BLED score is calculated by adding the specified points for each of the conditions listed. [\[R10-6394\]](#)

[figure not shown]

[figure not shown]

[figure not shown]

[figure not shown]

[figure not shown]

[figure not shown]

[figure not shown]

[figure not shown]

[figure not shown]

#### **9.4 DATA SOURCES**

The data source for this project will be data from MarketScan, a research claims database from commercial employer-sponsored health plans, through December 2014.

## **9.5 STUDY SIZE**

[figure not shown]
This study will identify covariates that represent potential confounding variables among dabigatran and warfarin users within a sampled population. The ability to identify a covariate and the precision for estimating potential confounding from the covariate will depend on the numbers of patients from whom electronic medical record data is extracted, and features of the covariate itself, such as how certain it is to be recorded in the medical record and whether binary (yes/no) or other.

The PS-matched dabigatran and warfarin initiators during Oct 2010– December 2013 period are approximately 20,000 each. Assuming that 5.5% of this study group will be linked to EMR, the EMR-linked subset up to Dec 2013 will consist of approximately 1100 patients in each exposure group.

The precision of estimated prevalence for a covariate obtained from the EMR depends on the prevalence of the covariate, and the sample size. With 10,000 dabigatran initiators, this study will estimate a patient characteristic that has a 10% prevalence with considerable precision (the 95% confidence interval will be 9.4% to 10.6%) ([Table 7](#)). A characteristic not captured in claims, but present in the medical record with a prevalence of 10% to 20% is plausibly a confounding variable and so this table enumerates characteristics with these prevalences. The table has not been extended below 10% since such lower prevalence characteristics have progressively less ability to produce meaningful confounding, so that while the study will have less precision to estimate such a characteristic, validation of the presence for such a low prevalence characteristic becomes unnecessary. At the other end of the range presented in the table, a characteristic with a prevalence above 20% will be identified with even greater precision, so that it also does not need to be depicted in the table.

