Population:	
Patients from an US health insurance database (electronic medical records) with a recorded diagnosis of atrial fibrillation without evidence of valvular etiology and at risk for stroke who initiate dabigatran or warfarin between October 2010 and December 2014 (This date range corresponds to the available matched cohort date range).
 
Inclusion criteria:
 
 
• A recorded diagnosis of atrial fibrillation.
 
• Initiation of anticoagulant medication (dabigatran or warfarin).
 
• At least 18 years of age on the date of anticoagulant initiation.
 
• CHA2DS2-VASc score ≥ 1
 
• Presence of electronic medical records (for the EMR-based subset)
 
 
Exclusion criteria:
 
 
• Patients with missing or ambiguous age or sex information.
 
• Patients with evidence of valvular disease.
 
• Patients with less than 12 months enrolment preceding the date of anticoagulant initiation.
 
• Patients with a dispensing of any oral anticoagulant during the 12 months preceding the date of anticoagulant initiation
 
• Patients with a nursing home stay during baseline
 
• Unmatched dabigatran/warfarin initiators
 
		

Name of company: Boehringer Ingelheim			
Name of finished medicinal product: Pradaxa® (Dabigatran etexilate), or warfarin			
Name of active ingredient: Dabigatran etexilate or warfarin			
Protocol date: 02 November 2016	Study number: 1160.219	Version/Revision: 1.0	Version/Revision date:

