Variables:	
Patient characteristics derived from insurance claims (claims-based covariates)
 
This study will characterize patients initiating oral anticoagulant medications with respect to select characteristics, some of which might be reflected differently in claims data compared to electronic medical records prior to and including the date of initiation. These characteristics from EMR data are usually treated as covariates but will be considered outcomes in this validation study.
 
These characteristics include:
 
Primary Outcomes
 
 
• Obesity
 
• Smoking
 
• Alcohol consumption
 
• Abnormal renal function
 
• Bleeding history or predisposition
 
• Renal function (estimated GFR)
 
• Serum Creatinine
 
• Abnormal liver function
 
 
Secondary Outcomes
 
 
• Duration of atrial fibrillation
 
• History of adherence
 
• History/duration of hypertension
 
• Uncontrolled Hypertension (for HAS-BLED)
 
• History/duration of CHF
 
• Prior TIA
 
• Diabetes
 
• Hyperlipidemia
 
		

Name of company: Boehringer Ingelheim			
Name of finished medicinal product: Pradaxa® (Dabigatran etexilate), or warfarin			
Name of active ingredient: Dabigatran etexilate or warfarin			
Protocol date: 02 November 2016	Study number: 1160.219	Version/Revision: 1.0	Version/Revision date:
Variables:	
 
HAS-BLED Score
 
Use of antiplatelets or NSAIDs (needed for HAS-BLED)
 
		
Data sources:	This study will be conducted within MarketScan data linked to electronic medical records.		
Study size:	
Study cohort: approximately 15,000 dabigatran initiators PS-matched to 15,000 warfarin initiators
 
EMR-linked subset: approx. 5.5% of the study cohort.
		

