**Table 8 Association between claims-based covariates and EMR linkage.**

Claims-based covariate	Dabigatran initiators		Warfarin initiators	
	N=		N=	
	Linked	Not linked	Linked	Not linked
Proportion (N)				
Age				
Age category 18-35				
Age category 36-64				
Age category 65-74				
Age category 75+				
Sex				
...				

*Objective 1: Descriptive*

The analyses for this objective will occur within the subpopulation of individuals with linked EMR data and will focus on describing the EMR-based clinical characteristics for the dabigatran and warfarin initiators. This table will provide an evaluation of the association between the EMR clinical characteristics and initiation of dabigatran or warfarin. [REDACTED]

The prevalence of each category for categorical characteristics and the mean and standard deviation for continuous characteristics will be calculated (as shown in the example [Table 9](#)). This analysis will aid in identifying EMR characteristics that are unbalanced across exposure groups and are therefore potential unmeasured confounders after PS matching.

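### Section 9.5 states the precision of EMR-based prevalences for 10,000 dabigatran initiators, but only about 1,100 per group are expected to be linked, so the stated 95% CI is about three times too narrow

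*Combined protocol and SAP*

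**What the plan says.** Section 9.5 states that the ability to identify a covariate, and the precision for estimating confounding from it, "will depend on the numbers of patients from whom electronic medical record data is extracted". It puts the matched cohort at Oct 2010 to "December 2013 period are approximately 20,000 each", assumes 5.5% linkage, and concludes that "the EMR-linked subset up to Dec 2013 will consist of approximately 1100 patients in each exposure group".

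The next paragraph deals with the prevalence of a covariate taken from the EMR. It says "With 10,000 dabigatran initiators, this study will estimate a patient characteristic that has a 10% prevalence with considerable precision", gives the 95% CI as 9.4% to 10.6%, and refers to Table 7, where this is the row with denominator 10,000.

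Section 9.7.1, Objective 1, fixes the analysis set for the EMR characteristics: "The analyses for this objective will occur within the subpopulation of individuals with linked EMR data". Section 9.11.2 likewise places most analyses in the linked subset.

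The abstract gives a different cohort size: "approximately 15,000 dabigatran initiators PS-matched to 15,000 warfarin initiators", with "EMR-linked subset: approx. 5.5% of the study cohort". Its population row sets the initiation window at October 2010 to December 2014 and adds: "This date range corresponds to the available matched cohort date range". Section 9.11.1 also uses December 2014.

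**The concern.** The sentence on precision is about what this study will achieve for EMR covariates, yet its denominator is about nine times the linked group projected one paragraph earlier. A reader would expect a 10% characteristic to be known to within about 0.6 points, when the planned data would give about 1.8 to 2.0 points per group.

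This matters for Table 9, which is meant to show which EMR characteristics remain unbalanced after matching. A reader who relies on the stated precision could take a small observed difference as good evidence of balance when an imbalance of 2 to 3 points is still compatible with the data.

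Two related problems add to this. The cohort sizes conflict: the longer window carries the smaller cohort, without explanation, and Section 9.5 gives no linked number for the window to December 2014. Also, precision is shown for one group's prevalence only, while the research question is whether characteristics differ between the two groups.

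**Working it through.** **Inputs.** Matched cohort per group: 20,000 (Section 9.5) or 15,000 (abstract). Linkage: 5.5% (both). Denominator used for the stated precision: 10,000 (Section 9.5). Prevalences: 10% and 20% (Table 7).

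**1. Reproduce the stated figure.** The exact (Clopper-Pearson) two-sided 95% interval for 1,000/10,000 is 9.42% to 10.61%, which rounds to the stated 9.4% to 10.6%. The same method reproduces Table 7's intervals at the other denominators from 100 to 100,000, for example 10/100 gives 4.9% to 17.6%. The method is therefore sound, and the fault is the denominator.

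**2. Linked number per group.**
- Section 9.5: 0.055 × 20,000 = 1,100
- Abstract: 0.055 × 15,000 = 825

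**3. What 10,000 linked patients would need.**
- At 5.5% linkage: 10,000 / 0.055 = 181,818 matched dabigatran initiators
- Or a linkage of 10,000 / 20,000 = 50%, or 10,000 / 15,000 = 67%

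One further calendar year of accrual cannot plausibly supply this.

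**4. Exact 95% intervals at the linked numbers.**

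| Prevalence | n = 10,000 | n = 1,100 | n = 825 |
|---|---|---|---|
| 10% | 9.42–10.61% | 8.29–11.93% | 7.98–12.19% (82 cases) or 8.09–12.32% (83 cases) |
| 20% | 19.22–20.80% | 17.67–22.49% | 17.32–22.90% |

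At 10% prevalence the width is 3.07 times that at 10,000 for n = 1,100, and 3.54 to 3.56 times for n = 825. The normal approximation agrees: √(10,000/1,100) = 3.02 and √(10,000/825) = 3.48.

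**5. One-group half-width at 10%,** 1.96 × √(p(1−p)/n): 0.59 points at 10,000, 1.77 at 1,100 and 2.05 at 825.

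**6. Half-width for the difference between two groups of equal size,** 1.96 × √(2p(1−p)/n), treating the groups as independent:

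| Prevalence | n = 10,000 | n = 1,100 | n = 825 |
|---|---|---|---|
| 10% | 0.83 points | 2.51 points | 2.90 points |
| 20% | 1.11 points | 3.34 points | 3.86 points |

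**7. Smaller points in the same section.**
- Table 7, denominator 1,000,000: √(0.1 × 0.9 / 1,000,000) = 0.030% and √(0.2 × 0.8 / 1,000,000) = 0.040%. The table prints 0.003% and 0.004%, ten times too small.
- The text says that prevalences above 20% are estimated more precisely, without saying on which scale. At n = 1,000 the s.e. rises from 0.95% to 1.26% between 10% and 20% prevalence, while the s.e. relative to the prevalence falls from 9.5% to 6.3%. The claim fits the relative scale, but Table 7 labels the absolute s.e. as precision.

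**The case against.** The sentence is conditional on 10,000 initiators, and its interval is right for that number, so it can be read as an illustration with an outdated denominator. The projected 1,100 stands in the paragraph before it. Table 7 has rows for 1,000 (8.2% to 12.0% and 17.6% to 22.6%) that are within about 0.1 point per limit of the values at 1,100. Section 9.9 warns that the EMR source may contain few dabigatran initiators. The data already exist, so this paragraph does not determine the linked number, and no visible test, margin or imbalance threshold uses the interval.

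Much of this stands, and it limits the weight of the point: the near-correct precision can be found in Table 7, and no decision rule is affected. It does not remove the inconsistency, because the text says what this study will estimate and directs the reader to the row for 10,000.

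The figure of 825 is less certain than 1,100. The abstract attaches no dates to its 15,000, and the documents do not show which cohort size is current. It is a scenario, not a correction. Parts of the analysis text are redacted, so the absence of between-group precision can be asserted only for what is visible. Adding it is an improvement to the plan; Objective 1 itself is descriptive.

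**Conclusion.** The concern holds. Section 9.5 claims a precision for EMR-based prevalences that its own projected linked subset cannot give. At 10% prevalence the 95% CI should be about 8.3% to 11.9% with 1,100 per group, or about 8.0% to 12.3% with 825, against the stated 9.4% to 10.6%. That is roughly 3.1 or 3.55 times wider.

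This rests on the documents' 5.5% linkage, on 20,000 or 15,000 matched patients per group, and on exact binomial intervals. The half-widths for the difference also assume two independent groups of equal size and equal prevalence. The 20,000 and 15,000 conflict, and the documents do not settle which applies.

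This should be corrected because it misstates what the study can show. It does not invalidate the design or any visible decision rule.

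**What to change.** - Reconcile cohort size and date window between Section 9.5 and the abstract, and state one expected linked number per group for the window actually used.
- Replace the 10,000 example with that number. Either cite Table 7's rows for 1,000, or add rows for 1,100 and 825.
- Add the 95% half-width of the between-group difference at 10% and 20% prevalence (2.5 and 3.3 points at 1,100; 2.9 and 3.9 points at 825).
- Correct the Table 7 s.e. entries at 1,000,000 to 0.03% and 0.04%.
- Say whether the statement about prevalences above 20% means relative or absolute precision.

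The cost is rewording and a recomputed table, with no extra patients or data. The stated precision becomes less favourable.
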